# 9.4 Reporting Deviations from the Statistical Analysis Plan

The detailed statistical analysis methodologies will be documented in the SAP. If there are any deviations from the originally planned analyses in the SAP, they will be fully described and justified in the protocol amendment(s) and/or final Clinical Study Report.

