1 INTRODUCTION

The purpose of this statistical analysis plan (SAP) is to outline the planned analyses to support the completion of the clinical study report (CSR) for protocol IG1405. Exploratory analyses not identified or defined in this SAP may be performed to support the clinical development program or manuscript. Any post-hoc or unplanned analyses performed and not identified in this SAP will be documented in the respective CSR.

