2 STUDY DESIGN AND OBJECTIVES

2.1 Study Design

This is a prospective, randomized, active-controlled, single-blind, parallel group clinical trial to evaluate the efficacy and safety of Fibrin Sealant Grifols (FS Grifols) as an adjunct to hemostasis during surgery in pediatric subjects.

Pediatric subjects (<18 years of age) requiring an elective (non-emergent), open (non-laparoscopic), pelvic, abdominal, or thoracic (non-cardiac) surgical procedure, wherein a target bleeding site (TBS) is identified and a topical hemostatic agent is indicated, will be eligible to participate in the clinical trial.

The study treatments will be applied on the cut parenchymous surface of a solid organ (i.e., liver) and in soft tissue (i.e., fat, muscle, or connective tissue).

[figure not shown]
A specific bleeding site will be defined as the TBS when it is determined by the investigator (the surgeon) that control of bleeding by conventional surgical techniques (including suture, ligature, and cautery) is ineffective or impractical and requires an adjunct treatment to achieve hemostasis.

When the TBS is identified, the investigator will record the precise anatomical location of the TBS, rate the intensity of the bleeding at the TBS (Grade 1-4 according to the 5-point validated bleeding severity scale [see Section 3 for the scale]) and record the size of the approximate bleeding surface (small, medium, large). For soft tissue surgery only, the investigator will also record the type of soft tissue (i.e., fat, muscle, or connective tissue). In this clinical trial, only subjects with a TBS with bleeding intensity of Grade 1 (mild) or Grade 2 (moderate) will be enrolled.

Subjects will be randomly allocated in a 1:1 ratio into 1 of 2 treatment groups: FS Grifols or EVICEL. The first 24 subjects to be enrolled in the study will be adolescents (age range 12 to 17 years). The term "enrolled" implies that the subject was actually randomized to and treated with either the FS Grifols or EVICEL. Enrollment will be monitored by surgery type to ensure at least 50% of the surgical procedures are hepatic. Subjects who are randomized and treated with any amount of study drug and withdrawn from the study will not be replaced.

The overall study schema is presented in the figure below:

Page 6 of 18

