4 GENERAL STATISTICAL CONSIDERATIONS

Statistical analyses and data presentations will be generated using SAS version 9.4 or higher.

Unless otherwise noted, for continuous variables, descriptive statistics will include the number of non-missing values, mean, standard deviation, median, minimum and maximum. For categorical variables, descriptive statistics will include counts and percentages per category. All statistical inference will be tested at 2-sided with α =0.05.

Unless otherwise noted, all data collected in the eCRFs or electronically transferred (such as central laboratory data) will be presented in data listings. Subjects will be identified in the data listings by subject number (which includes site number) and grouped by different treatment groups.

For table summaries, the data will be presented at the scheduled visits according to protocol. Any data collected at the unscheduled visits will be listed.

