4.3 Sample Size Considerations

The sample size of the study was estimated to provide sufficient power (at least 80%) to demonstrate the hemostatic efficacy of FS Grifols in parenchymous and soft tissue surgery.

Assuming that the true response rate is 80% for the FS Grifols group and 80% for the EVICEL group, it can be shown that a sample size of 172 subjects (86 subjects in the FS Grifols treatment group and 86 subjects in the EVICEL treatment group, with a 1:1 assignment ratio) would give a power of at least 80% to establish non-inferiority, with lower 95% CI for the ratio of the proportion of subjects with hemostasis success by 4 minutes in the 2 treatment groups (FS Grifols relative to EVICEL) above 0.80.

The approximate number of subjects planned to be randomized according to age range will be as follows:

Grifols Worldwide Operations, Ltd Page 12 of 18

- Adolescents (12 to 17 years): approximately 100
- Children (2 to 11 years): approximately 50
- Infants and toddlers (28 days to 23 months): approximately 16
- Preterm (up to gestational age <37 weeks) and term newborn infants (0 to 27 days): approximately 6

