9 EFFICACY ANALYSIS

The efficacy analyses will be performed using the mITT population. Additionally, the primary efficacy endpoint of the proportion of subjects achieving hemostasis by 4 minutes at TBS will be analyzed using the PP population (if different from mITT population). As sensitivity analysis, the primary efficacy endpoint will be analyzed using ITT population. For subjects in both treatments in the ITT population who do not meet the intra-operative criteria and do not receive the study treatment, they will be deemed not achieving hemostasis for the primary efficacy endpoint.

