9.1 Primary Efficacy Analysis

The primary efficacy variable is the proportion of subjects achieving hemostasis by T₄ based on its nominal scheduled time point at TBS.

Assuming that T is the response rate for the FS Grifols treatment group, C is the response rate for the EVICEL group (control group), M is the pre-specified non-inferiority margin.

The null hypothesis (H_0) is: Risk Ratio $(T/C) \le 1$ -M and

the alternative hypothesis (H₁) is: Risk Ratio (T/C) \geq 1-M,

where 1-M is 0.8.

The primary efficacy endpoint will be analyzed using Cochran-Mantel-Haenszel (CMH) test stratified by type of surgery (i.e., parenchymous surface of liver versus soft tissue surgery). The ratio of proportion (RR_{pooled}) of subjects meeting the primary efficacy endpoint in the two treatment groups (FS Grifols relative to EVICEL) and its two-sided asymptotic 95% confidence interval (CI) will be provided:

$$RR_{pooled} = \frac{\sum_{i} a_{i} * m_{0i} / N_{i}}{\sum_{i} b_{i} * m_{1i} / N_{i}}$$

The asymptotic 95% confidence interval of RR_{pooled} is calculated as:

Lower limit =
$$\exp\{\ln(RR_{pooled}) - Z_{\alpha/2} * SE\}$$

Upper limit =
$$\exp\{\ln(RR_{pooled}) + Z_{\alpha/2} * SE\}$$

Where the standard error (SE) is calculated as:

Grifols Worldwide Operations, Ltd Page 15 of 18
$$SE = \sqrt{\frac{\sum_{i} (n_{1i} * m_{1i} * m_{0i} - a_{i} * b_{i} * N_{i}) / N_{i}^{2}}{(\sum_{i} a_{i} * m_{0i} / N_{i})(\sum_{i} b_{i} * m_{1i} / N_{i})}}$$

where a_i , b_i , c_i , d_i , n_{1i} , n_{0i} , m_{1i} , m_{0i} , and N_i are the number of subjects defined in following table; i = 1 or 2 according to different types of surgeries (i.e., parenchymous surface of liver or soft tissue surgery).

		FS Grifols	EVICEL	Total
Hemostasis	Yes	$a_{\rm i}$	b_{i}	n_{1i}
achieved?	No	c_{i}	d_i	n_{0i}
Total		m_{1i}	m _{0i}	Ni

The non-inferiority will be deemed to have been demonstrated if the lower limit of the 95% CI exceeds 0.8. After the non-inferiority of FS Grifols to EVICEL is established, its superiority may be additionally claimed if the 95% CI for the ratio is entirely above 1.

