In this study, 2 types of applicator devices are used to apply FS Grifols (Fibrijet® device up to 30 November 2019, VistaSealTM Dual Applicator thereafter). A sensitivity analysis for the primary efficacy endpoint using mITT will be performed for the subgroups based on the use of different applicators, to compare FS Grifols-treated subjects with either type of applicator device vs the Evicel treatment group. A subgroup analysis by surgery type will also be provided for this by applicator type analysis.

If any missing hemostatic assessment at TBS at T₄ for a randomized subject occurs, it will be treated as non-hemostasis at TBS at T₄ for the subject in the primary efficacy analysis. A sensitivity analysis with non-missing observational hemostatic assessment at TBS at T₄ will be performed.

Considering that the hemostasis assessment may not be performed exactly at the scheduled time point, as supportive analyses, the primary efficacy variable based on the time window below will also be analyzed using the CMH test. The hemostasis assessment data at each time point will be classified into the appropriate category based on the time window in the table below, according to the elapsed time of hemostasis assessment from the start of initial treatment application (T_{Start}) to T₄, T₇ and T₁₀ time points in eCRF.

Scheduled Event	Time Window (MM:SS)
T ₄ (4 minutes from start of application)	<=4:10
T ₇ (7 minutes from start of application)	>=4:11 to <=7:10
T_{10} (10 minutes from start of application)	>=7:11 to <=10:10

Grifols Worldwide Operations, Ltd

Page 16 of 18

If multiple hemostasis assessments fall within the same time window, for purpose of the supportive analyses, the following two scenarios will be considered:

- (a) the first hemostasis assessment will be selected;
- (b) the last hemostasis assessment will be selected.

If there is no hemostasis assessment within a specific time window, the last hemostasis assessment within the previous time window will be carried forward. If there is no hemostasis assessment within the first time window (\leq =4:10), the hemostasis assessment will be deemed non-hemostasis success at T₄. The hemostasis assessment with the elapsed time from T_{Start} greater than 10 minutes and 10 seconds will be classified into the period that is after the 10-minute observational period and before the T_{Closure}.

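### Does the uneven error split of the asymptotic interval in SAP 9.1 leave the non-inferiority test unsound, or the plan short of a sensitivity analysis?

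*SAP*

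**What the plan says.** SAP 9.1 defines a Mantel-Haenszel pooled ratio of response rates, FS Grifols over EVICEL, stratified by type of surgery. It prints the standard error and the log-scale limits and calls the interval asymptotic. Protocol 9.1.2 and the synopsis also call it asymptotic. The decision rule is "The non-inferiority will be deemed to have been demonstrated if the lower limit of the 95% CI exceeds 0.8". Superiority may be claimed afterwards if the whole interval lies above 1.

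The error level is set once, in SAP 4: "All statistical inference will be tested at 2-sided with α =0.05". No one-sided level is given in either document.

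The primary endpoint is analysed in the mITT population and repeated in several ways:

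- **Population.** The per-protocol set is used if it differs from mITT, and SAP 9 adds "As sensitivity analysis, the primary efficacy endpoint will be analyzed using ITT population".
- **Data handling.** SAP 9.1 repeats the analysis with observed T4 assessments only.
- **Applicator.** SAP 9.1 compares each FS Grifols applicator type with EVICEL.
- **Timing.** SAP 9.1 states that "the primary efficacy variable based on the time window below will also be analyzed using the CMH test".

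None of these names a second interval method. SAP 1 allows further exploratory analyses and adds that "Any post-hoc or unplanned analyses performed and not identified in this SAP will be documented in the respective CSR".

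**The concern.** Non-inferiority is settled by the lower limit alone. A two-sided 95% interval is usually read as carrying 2.5% in each tail, so a reader may take the chance of a false non-inferiority claim to be at most 2.5%. For a ratio of proportions with a margin below 1, the log-scale asymptotic interval does not split its error evenly, and here the larger share falls on the side that decides the trial. A score interval, which estimates the variance under the margin hypothesis, is more even.

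If the result landed close to 0.8, the two methods could give different answers, and the asymptotic one would be the more favourable to FS Grifols. A score interval run only then would count as unplanned under SAP 1. At stake would be the credibility of a narrow pass.

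**Working it through.** **Inputs.** 86 subjects per arm and a margin of 0.8 (SAP 4.3 and 9.1); two-sided 0.05, so z = 1.96 (SAP 4); response rates from SAP 4.3: "Assuming that the true response rate is 80% for the FS Grifols group and 80% for the EVICEL group". At the margin, FS Grifols is therefore 0.8 × 80% = 64%. For the strata, SAP 2.1 says "Enrollment will be monitored by surgery type to ensure at least 50% of the surgical procedures are hepatic", while Protocol 4.2 says approximately 50%. I used 43 + 43 per arm, and 52 + 34 as an assumed case with about 60% hepatic.

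**1. The plan's own power figure.** With 43 per arm in each stratum and 80% in both arms, the expected counts are a = b = 34.4, n1 = 68.8 and N = 86. In the SAP standard error:

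- numerator: 2 × (68.8 × 43 × 43 − 34.4 × 34.4 × 86) / 86² = 6.88
- denominator: (2 × 34.4 × 43 / 86)² = 34.4² = 1183.36
- SE = √(6.88 / 1183.36) = 0.0762

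Power = Φ(−ln 0.8 / SE − 1.96) = Φ(0.2231 / 0.0762 − 1.96) = Φ(0.97) ≈ 83.3%. Exact enumeration of the SAP interval gives 82.6% stratified and 82.7% unstratified. The stated power of at least 80% is reproduced.

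**2. Error at a true ratio of 0.8.** I enumerated all 87 × 87 outcomes at 64% against 80%. The score method is Miettinen-Nurminen with factor N/(N−1).

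| Interval | Lower limit above 0.8 | Upper limit below 0.8 | Total | Power at 80/80 |
|---|---|---|---|---|
| Asymptotic, unstratified | 2.86% | 2.01% | 4.87% | 82.7% |
| Score, unstratified | 2.47% | 2.37% | 4.84% | 80.2% |
| SAP formula, 43 + 43 (exact) | 2.87% | 2.00% | 4.87% | 82.6% |
| SAP formula, 52 + 34 (simulated) | 2.89% | 2.02% | 4.91% | 82.7% |

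The asymptotic total stays below 5%. The lower-tail difference between methods is 2.856 − 2.468 = 0.39 points.

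**3. Would the score method guarantee 2.5%?** Over all 81 pairs of arm sizes from 83 to 91, the asymptotic lower tail is 2.74% to 3.06% and the score lower tail 2.33% to 2.57%. The score tail exceeds 2.5% in 16 of the 81 pairs. It is closer to 2.5%, but it is not bounded by it.

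**4. How often would the decision differ?** For EVICEL counts of 60 to 78 out of 86, the FS Grifols count needed is the same in 11 of 19 cases and one higher under score in 8. Example, 65/86 against 69/86: ratio 65/69 = 0.942, ln = −0.0597, SE = √(1/65 − 1/86 + 1/69 − 1/86) = 0.0814. The lower limit is exp(−0.0597 − 1.96 × 0.0814) = 0.803. The score limit is 0.796.

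The asymptotic limit passes and the score limit fails in 0.388% of trials at a true ratio of 0.8, and in 2.514% when both products are at 80%. The reverse has negligible probability. The split result is thus 2.514 / 0.388 ≈ 6.5 times as likely under equality as at the margin. Over the 81 pairs, disagreement under equality runs from 2.0% to 4.3%.

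**5. Is the method a departure from the programme?** Protocol 2.2.1.2 and 2.2.1.3 report ratios for the two earlier Surgicel-controlled trials.

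- 103/111 against 91/113: ratio 1.152, SE = √(1/103 − 1/111 + 1/91 − 1/113) = 0.0533, limits exp(0.1417 ± 0.1044) = 1.038 and 1.279.
- 96/116 against 84/108: ratio 1.064, SE = √(1/96 − 1/116 + 1/84 − 1/108) = 0.0666, limits exp(0.0621 ± 0.1306) = 0.934 and 1.213.

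Both match the reported limits to three decimals. The interval in SAP 9.1 is the stratified form of the same method.

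**The case for a change.** The best case for acting accepts that no stated level is breached. Its argument is that the error is larger on the side that decides the trial, that every disagreement of any weight favours FS Grifols, and that a score interval specified before unblinding would cost one paragraph and no power. The SAP already plans supportive analyses down to a ten-second allowance around T4, and Protocol 9.4 leaves room for more: "The detailed statistical analysis methodologies will be documented in the SAP".

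The facts in this case stand. So does a further point: a pass that the score limit does not confirm is weaker evidence than a pass in general. Any pass is 82.69 / 2.856 ≈ 29 times as likely under equality at 80% as at the margin, against about 6.5 times for the split result.

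The conclusion does not follow. With the decision left on the asymptotic interval, the lower-tail rate remains 2.86% and the claim is made on the same data as before. The second interval would carry no decision weight, and no rule would say what to conclude from a split result. The planned repeat analyses address doubts about the data: who is analysed, what is missing, when the assessment was made and which applicator was used. Nothing in the documents requires the interval formula to be varied as well, and the same remark could be made of any plan that names one interval. If a result did fall within a responder of the boundary, SAP 1 already allows the extra calculation, with disclosure in the study report.

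Moving the decision itself to the score limit would affect the lower tail, but it is a trade. Power falls from 82.7% to 80.2% at 86 per arm, and the score method gives only 78.7% at 85 per arm.

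**Conclusion.** The concern does not hold. The interval is correctly specified, openly labelled and consistent with the earlier trials. It meets the only error level the documents set: 4.87% against 5%. The imbalance is real but small, 0.39 points in the lower tail compared with a score interval. The proposed addition would change no conclusion, error rate or power. Using one interval rather than the other is a choice of method.

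This rests on the plan's 80% EVICEL rate. With 43 per arm in each stratum and EVICEL between 70% and 95%, the lower tail runs from 2.72% to 3.84% and the total from 4.78% to 5.05%, so the total passes 5% only at the top of that range, and by 0.05 points. Had either document promised a one-sided 2.5% level, the lower tail would exceed it and the matter would have to be reopened. Neither does.

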# 4.3.2 Randomization

Subjects satisfying all pre-operative enrollment criteria will be randomized in 1:1 ratio into the FS Grifols or EVICEL treatment groups. Randomization will be stratified by type of surgery (i.e., parenchymous versus soft tissue surgery) and age groups (i.e., 12-17 years, 2-11 years, 28 days-23 months, and 0-27 days). The investigator site pharmacy will use an Interactive Response Technology (IRT) system to obtain the randomization number and the corresponding assigned treatment (FS Grifols or EVICEL).

At the beginning of the surgical procedure, before any TBS is identified, all materials needed for FS Grifols or EVICEL application will be ready for use. If the subject meets the intra-operative eligibility criteria defined in Section 5.1 and Section 5.2, a randomization number will be recorded in the subject's source documents and electronic Case Report Form (eCRF). If the subject does not meet the intra-operative eligibility criteria, the study drug prepared by the pharmacist will remain unused and discarded according to the respective site standard

procedures. In this case, the IRT system will automatically assign the same treatment to the next subject enrolled in the same stratum.

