For primary efficacy endpoint, subgroup analyses will be provided for surgery type, age group, gender, race, baseline TBS bleeding intensity, and TBS size category.

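### Minor: the by-applicator sensitivity analysis sets FS Grifols subjects from one side of a dated device change against an EVICEL group from both sides, so each ratio can carry age-mix or calendar drift

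*SAP*

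**What the plan says.** SAP 9.1 records that FS Grifols was applied with two devices over the trial: the Fibrijet "device up to 30 November 2019, VistaSealTM Dual Applicator thereafter". It plans an mITT sensitivity analysis of the primary endpoint in subgroups formed by applicator, "to compare FS Grifols-treated subjects with either type of applicator device vs the Evicel treatment group". It adds: "A subgroup analysis by surgery type will also be provided for this by applicator type analysis". No period limit is placed on the EVICEL group, here or elsewhere.

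The primary method in the same section is the "Cochran-Mantel-Haenszel (CMH) test stratified by type of surgery". Neither age nor period is a stratum. Separately, for the primary endpoint, "subgroup analyses will be provided for surgery type, age group, gender, race, baseline TBS bleeding intensity, and TBS size category"; these are not crossed with applicator.

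Three other statements bear on the point:
- SAP 2.1: "The first 24 subjects to be enrolled in the study will be adolescents (age range 12 to 17 years" (enrolled means randomized and treated).
- SAP 4.3: "Adolescents (12 to 17 years): approximately 100", of 172 in all. Protocol 9.2 allows 50 to 100.
- Protocol 4.3.2: "Randomization will be stratified by type of surgery (i.e., parenchymous versus soft tissue surgery) and age groups". Allocation is 1:1.

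**The concern.** Randomization supports two comparisons: the whole of each arm over the whole trial, and the two arms within one period. It does not balance early FS Grifols subjects against early plus late EVICEL subjects, which is what each by-applicator ratio does.

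Age mix is a mechanism that the documents themselves supply, because enrolment starts with adolescents only. Other drift over calendar time is possible but not documented. Neither is adjusted for. The age subgroups could show that an age gradient exists, but they would not correct the by-applicator ratios.

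This is the plan's only by-applicator efficacy analysis, so the two ratios are likely to be read side by side. Their EVICEL denominator is shared, so that contrast is essentially early against late FS Grifols. This is exact for crude ratios. It is approximate for the stratified ratio in SAP 9.1, where the EVICEL term is weighted by each subgroup's surgery mix.

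**Working it through.** **The plan's own figure.** SAP 4.3 claims at least 80% power with 86 per arm, 80% success in both arms and a ratio margin of 0.80. With SE of ln(RR) = sqrt(0.25/86 + 0.25/86) = 0.0762, where 0.25 = (1-0.8)/0.8, power = Phi(ln(1/0.8)/0.0762 - 1.96) = 83.3%. The claim reproduces and is not in question. The SAP gives no figure for the by-applicator analysis.

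**Inputs from the documents.** 172 subjects, 1:1; first 24 adolescent; adolescents A = 100 (SAP 4.3) or 50 (minimum in Protocol 9.2).

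**Assumed inputs.** No true treatment or device effect. n = 30 to 70 subjects treated by 30 November 2019, including all of the first 24. After those 24, adolescents arrive at a constant rate. Three success patterns by age: 88% in adolescents against 72% in younger subjects, 85% against 78%, and 75% against 84%. The documents give none of these.

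**Formulas.** Early adolescents = 24 + (n-24)(A-24)/148. Early ratio = success rate at the early age mix / success rate in the pooled EVICEL arm. The later ratio is formed in the same way.

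**Worked case: A = 100, 88%/72%, n = 30.** Pooled rate = (100 x 0.88 + 72 x 0.72)/172 = 0.8130. Early adolescents = 24 + 6 x 76/148 = 27.08. Early rate = (27.08 x 0.88 + 2.92 x 0.72)/30 = 0.8644. Early ratio = 0.8644/0.8130 = 1.063. Later adolescent share = 76/148, later rate 0.8022, later ratio 0.987.

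| A | Adolescent / younger success | Early ratio, n = 30 | Early ratio, n = 70 | Later ratio |
|---|---|---|---|---|
| 100 | 88% / 72% | 1.063 | 1.020 | 0.987 |
| 100 | 85% / 78% | 1.027 | 1.008 | 0.994 |
| 100 | 75% / 84% | 0.963 | 0.989 | 1.008 |
| 50 | 88% / 72% | 1.114 | 1.035 | 0.976 |
| 50 | 85% / 78% | 1.048 | 1.015 | 0.990 |
| 50 | 75% / 84% | 0.940 | 0.982 | 1.013 |

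Against same-period EVICEL, the expected ratio is 1.00 in every row.

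**General drift, for scale only.** If half of each arm is early and success moves from 75% to 85% in both arms, the ratios against all EVICEL are 0.75/0.80 = 0.94 and 0.85/0.80 = 1.06. Nothing in the documents shows drift of that size.

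**Precision.** SE of ln(RR) at 80% success = sqrt(0.25/n1 + 0.25/n2):

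| FS Grifols subgroup | Against 86 EVICEL | Against same-period EVICEL |
|---|---|---|
| Early, 15 | 0.140 | 0.183 |
| Early, 35 | 0.100 | 0.120 |
| Later, 71 | 0.080 | 0.084 |
| Later, 51 | 0.088 | 0.099 |

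**Bias against variance.** Mean squared error on the log scale = ln(ratio)^2 + SE^2 for the planned comparison, and SE^2 for the same-period one. In the worked case this is 0.023 against 0.033. In the worst early case (A = 50, n = 30, ratio 1.114) it is 0.0312 against 0.0333. The planned comparison is lower in all 24 combinations (12 scenarios, two devices), though the closest, the later device in that same scenario, is nearly a tie (0.00702 against 0.00704).

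If the SEs use each scenario's own rates, one combination reverses, the worst early case. Planned: ln(1.114)^2 + (0.1464/0.8536)/15 + (0.2335/0.7665)/86 = 0.0116 + 0.0114 + 0.0035 = 0.027. Same-period: 2 x 0.0114 = 0.023.

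**The case against.** The strongest reply is that pooling EVICEL is a defensible trade of bias for precision. That largely stands. Using SEs at 80% success, the early-device bias is 0.08 to 0.77 of a standard error and below 0.5 in all but one scenario. The later-device ratio stays within 0.976-1.013, and the later device is the only FS Grifols applicator described in the current protocol (4.4.1.1, 4.4.3). A reader might infer that same-period controls should replace the planned comparison; the mean squared errors do not support that. They cover only the modelled age mechanism, however, not arbitrary calendar drift.

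It is also fair that little depends on the result. It is labelled a sensitivity analysis, carries no decision rule, and no device-against-device test is planned. The number treated before the change and the success rates by age are not in the documents, and the only documented link between age and time is 24 subjects, about 12 per arm.

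It could further be said that SAP section 1 already permits analyses it does not define, provided they are reported as unplanned. That allows a same-period comparison but does not pre-specify it, and a comparison chosen after the results are seen is worth less.

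Finally, a reader might infer that same-period EVICEL subjects are left out. They are not: they are part of the planned comparator, only not analysed separately.

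**Conclusion.** The point holds as a minor one. The by-applicator ratios are not concurrent randomized comparisons, and nothing else in the plan corrects them. Size and direction are unknown, and the bias is zero if response does not vary with age or period. Under the assumed inputs, with no true effect, the early-device ratio lies at about 0.94-1.11 and the later-device ratio at 0.98-1.01.

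Two stronger readings are not supported. The primary non-inferiority result is not affected, because it compares both randomized arms over the whole trial. Nor would a same-period comparison isolate a device effect: device and period coincide, so a device effect cannot be told from a treatment effect that changes with period or age mix.

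**What to change.** Keep the planned analysis. Add to SAP 9.1 that each applicator subgroup is also compared, descriptively, with EVICEL subjects randomized in the same period (up to 30 November 2019, or thereafter), stratified by surgery type, and that age group is tabulated by treatment and period. State two limits beside the result: it is less precise, and device and period cannot be separated.

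For the surgery-type breakdown, same-period counts and percentages are enough. With 30 early subjects, half of them hepatic, each cell holds about 7 or 8 per arm, and the early SE would rise from 0.198 to 0.258. A formal contrast of the two devices, such as a ratio of the two same-period risk ratios, is not worth adding: its 95% interval would run from about 0.67 to 1.48 with 15 per arm early, or 0.74 to 1.36 with 35.

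The cost is a short SAP addition, a date filter and a few lines of output. No new data are needed. The price is precision: the early-period SE of ln(RR) rises from 0.140 to 0.183 with 15 per arm, or from 0.100 to 0.120 with 35. That is why the same-period result belongs beside the planned one and not in its place.
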